5.0 STUDY COHORT

1. Population

Recruitment of 450 WLWH aged 18-45 years is being performed by research staff at 10 sites across Canada. The 450 WLWH will be randomized 1:1 to two groups:

- 1) Three doses of 9vHPV vaccine at the routine dosing schedule of 0/2/6 months.
- 2) Three doses of 9vHPV vaccine at an extended dosing schedule of 0/6/12 months.

Inclusion Criteria

- Has a confirmed diagnosis of HIV infection
- Has a cervix (not have had their uterus removed)
- Age 18-45 years
- Not pregnant, and not trying to become pregnant
- Able to communicate in English if adequate translation is not available

Exclusion Criteria

- Unable to give fully informed consent
- Allergy to the vaccine or its components
- Prior receipt of any HPV vaccine.

Females aged <18 are excluded because all children, including those with HIV, are vaccinated in adolescent programs in Canada leaving very few eligible under that age. Further, we seek to inform the use of 9vHPV vaccine beyond adolescent program ages. The upper age limit of 45 years was chosen based on vaccine licensure as the 9vHPV vaccine is currently authorized for use in females ages 9-45.

Women will not be excluded based on baseline HPV immune status. All women can benefit from vaccination as they are virtually all seronegative for at least one 9vHPV type. Also, HPV seronegativity is not required for vaccination programs, thereby making our findings most relevant to vaccination programs, which would be conducted without a seronegativity requirement. We will assess baseline HPV immune status for use in post hoc outcomes analysis.

2. Randomization

Randomization will be stratified by site using permuted blocks of random size. A CIHR Canadian HIV Trials Network (CTN) statistician will computer-generate random allocations, which will be uploaded to a password-protected webpage. When an eligible consenting participant is identified, the webpage will issue a study identification number and vaccine regimen allocation. An automated audit trail will track date and time of transactions along with study identification number, stratum, and allocation. No placebo will be used as the primary aim of this study is to assess non-inferiority to different 9vHPV vaccine dosing regimens, not to compare outcomes to unvaccinated women.

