7.2.1 Suspension of Study Procedures in Pregnancy

In the event of a pregnancy during the study, the investigative site is to notify [name] at the Study Coordinating Centre using a pregnancy reporting form as soon as the investigative site is made aware of the pregnancy. Following the resolution of the pregnancy, the investigative site will provide an update to the Pregnancy Reporting Form and inform the Study Coordinating Centre.

Study vaccination is to be suspended in pregnant participants and may be resumed at the resolution of pregnancy. All other study procedures may continue.

If a participant has a positive pregnancy test as part of the study visit, the clinic doctors or nurses will be notified and they will let the participant know about the result. If the participant receives a positive test outside of the clinic, they are asked to let the team know. Following the diagnosis of pregnancy, study vaccination will be temporarily stopped, and participants will be invited to resume vaccination at the same point that it was stopped, 1 month after the conclusion of the pregnancy if they choose to do so.

Pregnant participants will be invited to sign a Pregnancy Consent Form.

Information to be collected following signing of the Pregnancy Consent includes:

- estimated date of delivery
- the outcome and mode of delivery
- any important diagnoses associated with the pregnancy and delivery
- the date of birth or pregnancy loss
- the gestational weeks at birth or pregnancy loss
- infant's sex and weight
- infant's APGAR scores

- if the infant was required to stay in hospital longer than usual, and if so, what the cause was

3. Summary of Study Visits

Table 1A. Schedule of Visits (Routine Group: Follows Routine Vaccine Schedule)

	Informed Consent	Pregnancy Test	9vHPV Vaccine	Blood Draw	HPV DNA Swab ^a	AE Assessment	Ongoing Medical History	HPV Self-Sampling Questionnaire
Month 0	X	X	X	X ^c	X	X	X	X ^b
Month 1				X		X	X	
Month 2		X	X			X	X	
Month 6		X	X		X	X	X	
Month 7				X		X	X	
Month 12					X	X	X	
Month 24				X	X	X	X	X

^aSelf-sampling where acceptable to participant, ^b Pre-HPV-swabs, ^c Pre-vaccination

Table 1B. Schedule of Visits (Extended Group: Follows Extended Vaccine Schedule)

	Informed Consent	Pregnancy Test	9vHPV Vaccine	Blood Draw	HPV DNA Swab ^a	AE Assessment	Ongoing Medical History	HPV Self-Sampling Questionnaire
Month 0	X	X	X	X ^c	X	X	X	X ^b
Month 1				X		X	X	
Month 2								
Month 6		X	X	X ^c	X	X	X	
Month 7				X		X	X	
Month 12		X	X		X	X	X	

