To determine if 2 doses of 9vHPV vaccine are non-inferior to 3 doses in WLWH, we will evaluate serologic response by comparing peak anti-HPV16/18 GMTs individually with 95% CI at 7 months in both groups using linear regression, adjusted for HIV viral load, CD4+ T cell count, and age.⁴⁶ We will similarly compare seroconversion rates in the two groups using logistic regression. Adjusting for age and HIV clinical parameters instead of stratifying by them (they are also unlikely to be importantly imbalanced in a trial this size) can improve sensitivity/power.⁴⁶ Using immunobridging,^{47,48} we will also compare the rate of seroconversion and peak anti-HPV GMTs to previously published two-dose 4vHPV responses in girls and women without HIV²³ and previously published three-dose 9vHPV responses in girls and women without HIV using logistic regression for seroconversion rates and one-sample t-tests for GMT comparisons.^{18,49} Immunobridging is a highly accepted method of evaluating HPV vaccines in different groups when a correlate of protection is unknown and efficacy endpoints such as cervical dysplasia take many years to develop. Level of antibody response after two doses will be described by clinical and demographic variables (age, CD4 count, HIV viral load, HPV DNA or antibody positivity at baseline, and lifetime number of sexual partners) using general linear models.

4. Secondary Analyses

1. To compare differences in antibody persistence, longitudinal GMTs will be compared between the two groups (routine vs. extended dosing interval) to determine if there are differences in the rates of antibody persistence at month 24. We will use mixed-effects linear regression on the log-transformed titers to estimate the rate of decline of antibody titers by time since first vaccine dose. Differences in rates will be compared directly using an interaction term between group and time.

2. To evaluate HPV self-sampling acceptability, quantitative survey results will be summarized as frequencies. Comparisons among subgroups (e.g. by age, region, cultural background, and gender) will be conducted using linear regressions.

5. Exploratory Analyses

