Subgroup analyses by gender (woman, gender-diverse) will be conducted if sample size allows, examining differences in all outcomes by gender. Primary and secondary analyses will be analyzed by clinical and demographic variables including: age, ethnicity, region, CD4+ T cell count, HIV viral load suppression (vs. unsuppressed), and HPV DNA or anti-HPV antibody positivity at baseline.

7. **Sample Size Calculations**

The sample size was calculated based on the primary evaluation of non-inferiority of the immunologic response to 2 vs. 3 doses of 9vHPV vaccine. For ethical reasons, all 2 dose recipients will eventually receive a third dose but we used a dose ranging study design to achieve this end. Using a one-sided alpha = 0.025, a non-inferiority margin of 0.5 based on benchmarks set by Merck for other immunobridging studies leading to licensure,⁴³ a standard deviation of 1.379 calculated from HPV16 GMTs in our prior cohort of WLWH, and 80% power, we would require 205 participants per group (total: 410). Given an anticipated dose completion rate of 90% based on our prior experience, we aim to recruit 225 participants per group to achieve power to detect non-inferiority in peak 2 vs. 3 dose GMT.

At 6 of our 10 sites, there are >900 WLWH who are unvaccinated and eligible for this study, suggesting there are likely ~1800 eligible women at all sites. We therefore anticipate being able to achieve the target sample size of 450 given that 90% of eligible WLWH screened in our precursor study were enrolled.

14.0 **DATA MANAGEMENT**

The data safety and monitoring committee (DSMC) will be coordinated through established processes by the CTN and will function at pre-specified intervals to monitor the conduct and progress of the trial, evaluate the accumulating study data including all serious adverse events, recommend protocol changes, alert trial leaders to emerging procedural or ethical issues, and monitor enrolment to ensure timely conduct of the trial. All up to date adverse events will be reported to the DSMC at each meeting to ensure participant safety. All other data including immunogenicity, efficacy, and self-sampling acceptability will be reported to the DSMC as it becomes available throughout the study for assessment of study conduct and progress. Reports from the data management process will be provided to the DSMC to ensure data quality.

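### Adding type-specific baseline anti-HPV titre and site to the fixed month-7 model would be a nearly free gain in precision and calibration; leaving them out is not a validity error

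*Protocol*

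**What the plan says.** - **Model.** Section 13.3 compares month-7 titres for HPV16 and HPV18 separately, "in both groups using linear regression, adjusted for HIV viral load, CD4+ T cell count, and age". Section 13.5 item 1 repeats the same three covariates for the other seven vaccine types.
- **Reason for adjusting.** Section 13.3 defends "Adjusting for age and HIV clinical parameters instead of stratifying by them" on the ground that it can raise sensitivity or power.
- **Prior antibody.** Section 5.0 item 1: "Women will not be excluded based on baseline HPV immune status". Tables 1A and 1B (section 7.3) schedule a month-0 blood draw in both arms, footnoted as taken before vaccination. Sections 7.5.5.1 and 12.1 send one aliquot of each serum sample for the nine-type competitive Luminex assay.
- **Planned use of baseline status.** Section 5.0 item 1: "We will assess baseline HPV immune status for use in post hoc outcomes analysis". Section 13.3, however, plans general linear models that describe the two-dose response by baseline antibody positivity among other variables. Section 13.6 lists "HPV DNA or anti-HPV antibody positivity at baseline" as a subgroup factor for the primary and secondary analyses.
- **Site.** Section 5.0 item 2: "Randomization will be stratified by site using permuted blocks of random size". Section 5.0 item 1: "Recruitment of 450 WLWH aged 18-45 years is being performed by research staff at 10 sites across Canada". No analysis model in section 13 names site; only region appears, as a subgroup variable (13.6) and in the self-sampling comparisons (13.4).

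**The concern.** The baseline titre of the same type is a pre-treatment measurement of the outcome itself, so it is an obvious candidate covariate in a trial that enrols both seropositive and seronegative women. The protocol says it adjusts in order to gain power, and it treats baseline antibody as a possible predictor elsewhere. Yet it leaves it out of the one comparison where it would narrow the interval. Any chance difference between arms in prior antibody also passes into the estimated titre ratio.

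Site is a separate matter. Stratified blocks balance the arms within site, so the true sampling error of the difference no longer contains the between-site variation. A model without site leaves that variation in the residual and reports a standard error that is larger than the true one.

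At stake is the width and calibration of the confidence interval that is set against the non-inferiority margin, not the validity of the comparison.

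**Working it through.** **Inputs.** From 13.7: SD 1.379, margin 0.5, one-sided alpha 0.025, power 80%, 205 evaluable women per group. From 5.0: 10 sites, 1:1 allocation. The protocol does not state the log base or the scale of the margin. I assume natural logs and show both readings of the margin: a difference of 0.5, or a ratio of 0.5 (ln 2 = 0.693). It gives no seroprevalence, no correlation between baseline and month-7 titre, and no between-site variance, so those enter as assumed ranges. I take 1.379 as the residual SD of the planned model.

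**1. The plan's own figure.** n per group = 2 × SD² × (1.960 + 0.842)² / margin², true difference zero.
- Margin 0.5: 2 × 1.902 × 7.849 / 0.25 = 119.4, so 120.
- Margin ln 2: 2 × 1.902 × 7.849 / 0.480 = 62.1, so 63.

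Neither gives 205. The stated n needs an unstated true difference (0.118 on the 0.5 margin) or a larger SD (1.81 on 0.5, 2.50 on ln 2).

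At 205 per group, SE = 1.379 × √(2/205) = 0.1362, and power = Φ(margin/SE − 1.960).
- Margin 0.5: Φ(3.671 − 1.960) = 95.6%.
- Margin ln 2: Φ(5.089 − 1.960) = 99.9%.

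**2. Baseline titre.** If it explains an extra share R² of the residual variance, the SE is multiplied by √(1 − R²). Half-width = 1.96 × SE.

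| Assumed extra R² | Residual SD | 95% CI half-width (ln) | As ratio factor | CI narrower by |
|---|---|---|---|---|
| 0 | 1.379 | 0.267 | 1.31 | – |
| 0.05 | 1.344 | 0.260 | 1.30 | 2.5% |
| 0.10 | 1.308 | 0.253 | 1.29 | 5.1% |
| 0.20 | 1.233 | 0.239 | 1.27 | 10.6% |
| 0.30 | 1.154 | 0.223 | 1.25 | 16.3% |

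On the 0.5 margin, power moves from 95.6% to Φ(3.671/√0.90 − 1.960) = 97% at R² = 0.10 and Φ(3.671/√0.70 − 1.960) = 99% at R² = 0.30. On ln 2 there is almost nothing left to gain.

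The same loss seen as imbalance: if mean baseline log titre differs between arms by one of its own standard errors, the estimate that omits it shifts by √R² × 0.1362. That is 0.316 × 0.1362 = 0.043 at R² = 0.10 and 0.548 × 0.1362 = 0.075 at R² = 0.30. This is random, not systematic.

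**3. Site.** Site-stratified blocks were simulated with 10 unequal sites, 410 women and 3,000 runs per setting. Each cell gives two values: baseline R² of 0, then 0.20. The model contained neither site nor baseline titre.

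| Assumed site share of variance | Mean reported SE / true SE | One-sided type I error | 95% CI coverage |
|---|---|---|---|
| 0.05 | 0.1358/0.1325 = 1.02; 0.1357/0.1330 = 1.02 | 0.025; 0.023 | 0.952; 0.952 |
| 0.10 | 0.1353/0.1303 = 1.04; 0.1353/0.1289 = 1.05 | 0.021; 0.020 | 0.962; 0.960 |
| 0.20 | 0.1344/0.1222 = 1.10; 0.1345/0.1250 = 1.08 | 0.019; 0.021 | 0.964; 0.964 |

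Each ratio carries Monte Carlo noise of about 1/√6000 = 1.3%. With no site variance the two ratios scatter around 1 (0.98 and 1.01).

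With site and baseline titre both in the model, coverage in the same six settings was 0.946 to 0.952. One-sided error was 0.025 to 0.031, with a Monte Carlo standard error of √(0.025 × 0.975/3000) = 0.003.

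**4. Cost if the terms explain nothing.** With site share and R² both zero, the mean reported SE was 0.1365 with the terms and 0.1362 without, an increase of 0.2%.

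**The case against.** Randomisation makes the three-covariate comparison valid, and adjusting for three plausible prognostic factors is an acceptable primary analysis. That stands, and it rules out several stronger readings.

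- *The error bars are too short because the stratification is ignored.* A reader might infer this, but the direction is the opposite. Omitting the stratum widens the interval, which is the safe direction for a non-inferiority claim.
- *Power rises from 80% to 82–92%, or the loss equals 5–43% more patients.* These figures follow if 80% is the true starting power and one R² covers baseline titre and site together. Neither holds. The stated SD and margin do not give 80% at 205 per group. Stratified randomisation has also already removed site variation from the true sampling error, so adding site corrects the reported standard error and adds little real precision.
- *Baseline immune status is ignored.* It is not: 13.3 and 13.6 both plan to use it. Those uses describe one regimen's response or split the sample, though, and do not adjust the comparison between arms.

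Two further points limit the size. All serology is assigned to one laboratory arrangement (12.1), which removes one source of site differences. And any gain from baseline titre must come on top of viral load, CD4 count and age.

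It can also be said that coding of low titres and pooling of sites belong in an analysis plan that is not shown. That is fair for the coding detail. The covariate list itself, however, is written out in the protocol, twice, and not left open.

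**Conclusion.** The point holds as an efficiency and calibration improvement of unknown size. The fixed covariate list leaves out a pre-treatment measurement of the outcome and the only stratification factor, although the protocol justifies adjustment by power and the data are already to be collected.

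The ranges of 2.5 to 16% for interval width and 2 to 10% for the reported standard error rest on assumed variance shares, natural logs and 1.379 as the residual SD; none of these is confirmed by the document. The effect on the non-inferiority conclusion may be modest. Surplus power is not a safe reason to forgo the gain, because the 205 per group is recovered only with an unstated true difference or a larger SD, and in either case precision would matter more.

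The *post hoc* label in 5.0 conflicts with the uses planned in 13.3 and 13.6. It is a minor inconsistency, but it should go: an adjustment for baseline antibody first introduced after results are seen would be open to the charge of being chosen from the data.

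**What to change.** 1. In 13.3 and 13.5 item 1, keep viral load, CD4 count and age, and add (a) the log baseline titre of the same HPV type, with a value fixed in advance for results below the assay cut-off, and (b) site, with small sites pooled under a rule fixed in advance.
2. In 5.0 item 1, replace the *post hoc* wording so that it agrees with 13.3 and 13.6 and with the new primary covariate.
3. Do not attach a power gain to this change until the sample size inputs in 13.7 have been reconciled.

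Cost: a line or two of model specification and no new samples or visits. With 410 evaluable women, the intercept, arm and three covariates (one term each) leave 405 residual degrees of freedom. One titre term and nine site terms use 10 of these, fewer if sites are pooled.

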3.0 OBJECTIVES

The overall goal of the study is to assess whether 2 doses of vaccine are non-inferior to 3 doses. Participants will be randomized 1:1 to receive 3 doses of 9vHPV vaccine at the routine vaccine schedule of 0/2/6 months or at an extended schedule of 0/6/12 months.

1. **Primary Objective**
 - 1) Determine whether peak anti-HPV16/18 geometric mean titers (GMTs) to 2 doses of 9vHPV vaccine are non-inferior to peak anti-HPV16/18 GMTs to 3 doses at month 7.
2. **Secondary Objectives**
 - 2) Compare the antibody persistence at month 24 between the routine and extended vaccine schedule.
 - 3) Elucidate the acceptability of HPV self-sampling among WLWH in Canada.

3. Exploratory Objectives

- 4) Determine whether peak anti-HPV6/11/31/33/45/52/58 GMTs from 2 doses of 9vHPV vaccine are non-inferior to those from 3 doses at month 7.
- 5) Assess peak anti-HPV16/18 GMTs to 1 dose at month 1.
- 6) Describe the incidence, type, and severity of adverse events in WLWH.
- 7) Elucidate the efficacy of 9vHPV vaccination up to month 24 (via persistent HPV infection with 9vHPV types, and cytological and histological HSIL).
- 8) Engage in a BC Cancer Registry linkage to investigate rates of pre-cancer or cancer diagnoses.
- 9) Investigate the role of viral and bacterial co-infection in the development of cervical dysplasia and vaccine breakthrough HPV infection in WLWH
- 10) Assess the uptake of HPV vaccination in WLWH aged 18-45 across Canada prior to study.

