At the month 2 visit, the following will be done:

- Assess ongoing consent.
- A brief assessment of vaccine contraindications (including temperature).
- A urine pregnancy test (regardless of age or sexual activity).
- Review of any changes in health status and/or medications.
- Review of any significant adverse events last study visit.
- The second of three HPV vaccine doses will be given.
- Instructions regarding the 14-Day Post-Vaccine Symptom Diary
- PLEASE NOTE: there will be no blood drawn at this visit.

4 weeks after the Month 2 visit, the study coordinator will contact the participant to review any adverse events occurring in the first 14 days following vaccination and any significant adverse events following this period. This will act as a safety follow-up, as participants will not be seen in-person again until Month 6.

Month 6

At the month 6 visit the following will be done:

- Assess ongoing consent.
- A brief assessment of vaccine contraindications (including temperature).
- A urine pregnancy test (for all participants regardless of age or sexual activity).
- Review of any changes in health status and/or medications.
- Review of any significant adverse events following this period.
- An HPV vaccine dose will be given (for the routine group, this will be the 3rd and final dose; for the extended group, this will be the 2nd dose).
- Instructions regarding the 14-Day Post-Vaccine Symptom Diary
- A self-collected vaginal swab for detection of HPV DNA, and a retention swab.
- PLEASE NOTE: there will be no blood drawn at this visit for the routine group; study bloodwork will be done for the extended group.

Month 7

At the month 7 visit the following will be done:

- Assess ongoing consent.
- Review of any changes in health status and/or medication.
- Review of all adverse events occurring in the first 14 days following vaccination and any significant adverse events following this period.
- Study bloodwork.

Month 12

At the month 12 visit, the following will be done in participants from the routine group:

- Assess ongoing consent.
- Review of any adverse events since last study visit.
- A brief physical assessment (weight).
- A review of any changes in health status and/or medications.
- A self-collected vaginal swab for detection of HPV DNA, and a retention swab.
- PLEASE NOTE: there will be no blood drawn at this visit.

At the month 12 visit, the following will be done in participants from the extended group:

- Assess ongoing consent.

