- A brief physical assessment (weight).
- A urine pregnancy test (regardless of age or sexual activity).
- A brief assessment of vaccine contraindications (including temperature).
- Review of any changes in health status and/or medications.
- Review of any significant adverse events since vaccination.
- A self-collected vaginal swab for detection of HPV DNA, and a retention swab.
- The third of three HPV vaccine doses will be given.
- Instructions regarding the 14-Day Post-Vaccine Symptom Diary
- PLEASE NOTE: there will be no blood drawn at this visit.

4 weeks after the Month 12 visit, the study coordinator will contact the extended group to review any adverse events occurring in the first 14 days following vaccination and any significant adverse events following this period. This will be act as a safety follow-up, as participants will not be seen in-person again until Month 24.

Month 24

At the month 24 visit, the following will be done:

- Assess ongoing consent.
- Review of any significant adverse events since last study visit
- A review of any changes in health status and/or medication.
- A short questionnaire regarding how the participant feels about self-collecting a vaginal swab for the purpose of HPV screening for cervical cancer.
- A self-collected vaginal swab for detection of HPV DNA, and a retention swab.
- Study bloodwork.

5. Study Procedures in Detail

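### The group-by-time test of antibody persistence does not compare decline rates, because the extended arm has a third dose at month 12 and no titre between months 7 and 24

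*Protocol*

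**What the plan says.** The first secondary objective (Protocol section 3.0) is: "Compare the antibody persistence at month 24 between the routine and extended vaccine schedule".

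For its analysis, section 13.4, item 1, first says that longitudinal GMTs will be compared between the groups. It then specifies mixed-effects linear regression on log-transformed titres, used "to estimate the rate of decline of antibody titers by time since first vaccine dose". The named test is: "Differences in rates will be compared directly using an interaction term between group and time". It gives no change point, no term for a later dose and no restriction to samples taken after the series is complete.

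The schedules in section 5.0 are:
- Routine: "Three doses of 9vHPV vaccine at the routine dosing schedule of 0/2/6 months".
- Extended: "Three doses of 9vHPV vaccine at an extended dosing schedule of 0/6/12 months".

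On blood draws, section 7.4.5 says of month 6: "there will be no blood drawn at this visit for the routine group; study bloodwork will be done for the extended group". For the extended arm at month 12 it says: "The third of three HPV vaccine doses will be given" and, in the same list, "PLEASE NOTE: there will be no blood drawn at this visit". The next in-person visit is month 24. Tables 1A and 1B agree with this.

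**The concern.** A decline rate for a completed series needs at least two titres after the last dose. The extended arm has one. The line joining its month-7 and month-24 titres starts from a 2-dose response, passes through a booster whose effect is never measured, and ends on a 3-dose response. Testing that line against the routine arm's month 7-24 line compares two different quantities.

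The interaction is the only significance test that item 1 names for the first secondary objective. A significant result could be reported as a difference in waning between schedules when it reflects only the later third dose.

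**Working it through.** The protocol gives no slope, sample size or power for this analysis, so there is no stated figure to reproduce. The check has two parts.

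**1. Structure, from the schedule alone**

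| | Routine | Extended |
|---|---|---|
| Doses (month) | 0, 2, 6 | 0, 6, 12 |
| Blood draws (month) | 0, 1, 7, 24 | 0, 1, 6, 7, 24 |
| Doses before the month-7 titre | 3 | 2 |
| Titres after the last dose | 2 (months 7, 24) | 1 (month 24) |
| Months from last scheduled dose to month 24 | 24 - 6 = 18 | 24 - 12 = 12 |

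With one post-series titre, the extended arm's post-series decline cannot be estimated on any time axis. Counting time from the last dose instead of the first would not help.

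**2. Size, under assumed decay**

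Assumptions, none of them in the protocol: after the last dose ln titre falls as k × ln(months since that dose), with the same k of 0.4-0.8 in both arms; the 3-dose peak P, one month after dose 3, is equal in both arms; the extended month-7 titre is r times the routine month-7 titre, with r of 0.6-1.0.

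- Routine slope, months 7-24: -k × ln 18 / 17.
- Extended: ln titre is P + ln r at month 7 and P - k × ln 12 at month 24, so the slope is -(k × ln 12 + ln r) / 17.

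Results:
- k = 0.6, r = 0.8: routine -(0.6 × 2.890)/17 = -0.102 per month; extended -(0.6 × 2.485 - 0.223)/17 = -0.075 per month. The ratio is 73%.
- Lowest ratio, k = 0.4, r = 0.6: (0.994 - 0.511)/1.156 = 42%.
- Highest ratio, r = 1.0, any k: ln 12 / ln 18 = 86%.

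**Where the sign turns.** The slopes are equal when k × ln 12 + ln r = k × ln 18, that is r = 1.5^k. This gives 1.5^0.4 = 1.18 and 1.5^0.8 = 1.38. Above that value the extended slope is the steeper one. For example, k = 0.6 and r = 1.5 give -(1.491 + 0.405)/17 = -0.112 against -0.102.

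**How often the test would reject with identical decay.** Take a constant decay of d ln units per month after the last dose, equal 3-dose peaks and r = 1. The routine change over months 7-24 is -17d. The extended change is -11d (months 13-24, from the same peak). The difference is 6d. Section 13.7 gives an SD of 1.379 (log base not stated; natural log assumed here) and 205 per group. With an assumed month 7 to month 24 correlation ρ, SE = 1.379 × √(2(1 - ρ)) × √(2/205).
- d = 0.05, ρ = 0.5: difference 0.30, SE 0.136, two-sided 5% rejection about 60%.
- d = 0.05, ρ = 0.7: SE 0.106, rejection about 81%.
- d = 0.10, ρ = 0.5: difference 0.60, rejection about 99%.

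**The case against.** **The objective concerns persistence at month 24, and item 1 opens by comparing longitudinal GMTs.** This stands. The month-24 contrast between randomised arms is valid, and a reader who infers that the secondary objective is lost goes too far. What fails is the decline-rate reading of the interaction, which is nevertheless the only test named.

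**An unseen SAP may settle which visits enter and how time is coded.** This stands in part. A reader might infer that one straight line runs through all draws, including the rise from baseline, and so gives positive slopes. Item 1 does not say which draws enter, and its reference to decline points to post-peak samples, so the text does not require that reading. But no SAP wording can recover a post-dose-3 peak that was never drawn.

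**The artefact need not favour the extended schedule.** This stands. A reader might infer that the test would always show slower decline there. That needs assumptions about the 2-dose and 3-dose peaks which the protocol does not supply.

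**Being 12 rather than 18 months from the last dose is part of the extended schedule.** This also stands. A reader might call it bias at month 24, but it belongs to the randomised comparison of schedules. It needs to be stated, not corrected.

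**A pre-dose blood draw at month 12 might seem to repair the analysis.** It would not. It adds no titre after dose 3, so extended-arm decline stays inestimable.

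**Conclusion.** The point holds in a limited form. The interaction in section 13.4, item 1, fits one slope per arm, and the extended slope is not a post-series decline rate. This follows from the dosing and blood-draw schedule and needs no assumption about decay.

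The size does rest on assumptions. With equal decay after the last dose, equal 3-dose peaks and a 2-dose/3-dose month-7 ratio of 0.6-1.0, the extended slope is 42-86% of the routine slope. In the constant-decay cases shown, the test rejects in about 60% to 99% of trials although decay is identical. If the month-7 ratio exceeds about 1.18-1.38, the slope contrast changes sign. The documents therefore support calling it uninterpretable, and do not support a claim of bias in a known direction.

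This should be fixed. It concerns one secondary analysis; the month-7 primary endpoint and the randomised month-24 contrast are unaffected.

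**What to change.** In section 13.4, item 1:
- Replace the slope interaction, as the test for this objective, with the adjusted month-24 GMT ratio (extended/routine) and its 95% CI. Take it from a mixed model on log titre with visit as a category and an arm-by-visit term. The month-6 draw exists in the extended arm only and so gives no between-arm contrast.
- Describe the result as a comparison of schedules 24 months after the first dose, when the arms are 12 (extended) and 18 (routine) months past the last scheduled dose. Do not call it a comparison of decline rates.
- Report month 7-24 decline for the routine arm only, as a description.

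The cost is analysis wording. No visit, blood draw or assay is added, and the sample size does not change.
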